15.3 Stratification Factors

N/a

15.4 Analysis of Secondary Endpoints

From a total of 100 NSCLC patients studied, we estimate that 30 will have an *EGFR* sensitizing mutation (exon 19 del/L858R), respectively, based upon prior prevalence data at our institution. Concordance between tumor and plasma genotyping results will be calculated using a Cohen's kappa. The potential clinical value of the ddPCR genotyping assay will be estimated using:

• Positive predictive value (PPV): To be clinically useful, the PPV must exceed 90% for the plasma assays for *EGFR* and *KRAS* mutations.

• Sensitivity: The sensitivity of each assay must exceed 70% to have clinical value.

• Efficiency: The turnaround time (TAT) between ordering the plasma genotyping and obtaining the result will be compared to the TAT for tumor genotyping. We will compute the turnaround time for each, and compare them using the Wilcoxon-test. To have maximal clinical value, the median TAT for plasma genotyping must be less than 3 days.

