1.3 Secondary Objectives

- Determine the time from study registration to treatment initiation using a rapid plasma genotyping strategy versus standard tumor genotyping.
- Ascertain the positive predictive value and false negative rate of plasma genotyping for patients with recently diagnosed advanced NSCLC among patients with tissue available for standard genotyping.

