Following initial validation of this assay in a small group of patients as described above, we retrospectively examined this assay in a larger group of metastatic NSCLC patients with EGFR sensitizing mutations (exon 19 del, L858R) and acquired resistance to EGFR kinase inhibitors. This study compared the test characteristics of our ddPCR-based plasma genotyping assay for the detection of both EGFR sensitizing and the T790M acquired resistance mutation in a cohort of 41 patients with advanced NSCLC who had undergone re-biopsy and standard tissue genotyping for comparison. This revealed 70% assay sensitivity for detection of EGFR T790M and a 93% assay specificity to T790M. In addition, a subset of 15 of these patients underwent serial plasma genotyping after beginning a new line of systemic/targeted therapy. This subset of patients underwent baseline plasma genotyping followed by repeat testing with each treatment cycle. Patients with a partial response to treatment uniformly exhibited decreased levels of *EGFR* cfDNA over time whereas patients without response exhibited stable or increased levels [Figure 2].¹⁴ These data indicate that this assay may also predict treatment outcome as early as 4 weeks after initiating treatment – potentially allowing early treatment modification.

We have subsequently initiated a prospective study of ddPCR-based plasma genotyping in a planned cohort of 340 NSCLC patients in order to assess its ability to accurately detect *EGFR* sensitizing (exon 19 del, L858R), T790M and *KRAS* G12X mutations. These patients include newly diagnosed patients, those with acquired resistance to kinase inhibitors and those undergoing a new line of subsequent treatment. The aims of this study include assessing both test characteristics compared to gold standard tissue genotyping performed on a biopsy specimen as well as correlating change in detectable levels of mutations

during treatment with radiographic response through serial blood testing. This study has accrued 250 patients thus far. Median TAT for plasma ddPCR is 3 days (range 1-5). Specificity of plasma ddPCR is 99% for 19 del/L858R (94/95) and 100% for *KRAS* (82/82), but lower for T790M at resistance (81%, 22/27). Sensitivity

[figure not shown]

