Figure 2: change in *EGFR* mutation copy number in advanced NSCLC patients with (A) and without (B) a partial radiographic response after initiating a new line of therapy (PR – partial response, SD – stable disease, PD – progressive disease per RECIST 1.1).

[figure not shown]

Figure 3: log-fold change in mutation copy number in advanced NSCLC patients correlates with radiographic response in patients treated with both standard chemotherapy and kinase inhibitors (per RECIST 1.1).

of plasma ddPCR is 75% for 19 del/L858R (73/97) and 73% for T790M (30/41) but lower for *KRAS* (62%, 16/26).

Taken together, these previous studies indicate that ddPCR-based plasma genotyping using our validated assay is able to detect *EGFR* sensitizing mutations (exon 19 del, L858R) in metastatic NSCLC with a

high degree of specificity and acceptable sensitivity. A positive result from this assay is thus highly specific for the presence of an *EGFR* mutation and clinically actionable given the very low likelihood of false positive results.

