3. PARTICIPANT SELECTION

3.1 Eligibility Criteria

Participants must meet the following screening criteria in order to enroll and undergo plasma genotyping on this study:

- 3.1.1 Histologically or cytologically confirmed metastatic NSCLC including recurrent disease
- 3.1.2 *EGFR* genotype must not be known. However, pending *EGFR* tumor genotyping is allowed.
 - 3.1.2.1 Participants with positive or pending EGFR mutation on plasma genotyping performed at the central lab are eligible for enrollment, and will not need to repeat initial plasma genotyping on study.

CONFIDENTIAL

3.1.3 Tissue must be available for genotyping or biopsy planned to obtain tissue for genotyping. Biopsy requirement may be waived if not technically feasible and plasma genotyping reveals an eligible *EGFR* mutation (exon 19 del/L858R). Determination of technical feasibility must be made independently of plasma genotyping results.

- 3.1.4 Participants must possess at least two of the following clinical characteristics which enrich for *EGFR* mutations:
 - smoked less than 10 pack years
 - Asian race
 - Adenocarcinoma (including adenosquamous carcinoma) on histology or cytology.
- 3.1.5 Participants must have measurable disease with at least one lesion that can be accurately measured in longest dimension as >2 cm with conventional imaging techniques or >1 cm with a spiral CT scan per RECIST v1.1.
- 3.1.6 Participants must have progressive, advanced cancer as defined by one of the following:
 - Newly diagnosed, untreated advanced disease
 - Newly diagnosed, untreated metastatic recurrence of earlier stage disease (previous treatment of early stage disease allowed).
 - Clinical determination of progressive disease on previous systemic therapy as evidenced by plan to change treatment. Any number of prior therapies are acceptable excluding previous EGFR kinase inhibitors.
- 3.1.7 Age 18 years or older.
- 3.1.8 ECOG performance status 0-2.
- 3.1.9 Participant must be able to understand and give consent to participate in the study.
- 3.1.10 Patient must be a candidate for systemic therapy with erlotinib based on clinical assessment. Patients must meet the following criteria before beginning therapy (Note: these are not required for initial study enrollment and plasma genotyping):
 - ECOG performance status of 0-2
 - Platelets >75
 - AST & ALT < 3x the upper limit of normal
 - Creatinine clearance > 30 mL/min by Cockroft-Gault
 - No other contraindication to erlotinib

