15.2 Sample Size/Accrual Rate

100 participants recruited over a 2 year period will undergo plasma genotyping for potential treatment with erlotinib on study. It is anticipated that approximately 30 patients will be positive for an EGFR (exon 19 del/L858R) sensitizing mutation by plasma. After recruitment of 50 patients is complete, the accrual rate and number of patients treated with erlotinib will undergo re-assessment for feasibility.

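### A PPV above 90% in this enriched cohort does not by itself show a PPV above 90% in the wider population that the secondary objective names, and specificity is not listed among the assay measures

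*Combined protocol and SAP*

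**What the plan says.** Section 15.4 lists Cohen's kappa, PPV, sensitivity and turnaround time as the measures of the assay's value. The PPV criterion reads "To be clinically useful, the PPV must exceed 90" percent, and it applies to both the EGFR and the KRAS plasma assay. It states no target prevalence, no confidence bound and no limit to a subgroup. Specificity is not on the list.

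The PPV objective in section 1.3 is stated "for patients with recently diagnosed advanced NSCLC", limited only to patients with tissue for standard genotyping. The synopsis words the objective for the same population, also without a smoking, race or histology limit.

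Eligibility is narrower. Criterion 3.1.4 reads "Participants must possess at least two of the following clinical characteristics which enrich for" EGFR mutations; the three characteristics are a light smoking history, Asian race and adenocarcinoma histology. Sections 1.1, 3.3 and 15.1 repeat that enrichment is intended.

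The accuracy figures are in section 2.3: "Specificity of plasma ddPCR is 99% for 19 del/L858R (94/95") and, for sensitivity, "of plasma ddPCR is 75% for 19 del/L858R (73/97"). On expected numbers, section 15.4 says "From a total of 100 NSCLC patients studied, we estimate that 30 will have an" EGFR sensitizing mutation and credits this to the institution's earlier prevalence data. Section 15.2 applies the same 30 to plasma results: "It is anticipated that approximately 30 patients will be positive for an EGFR (exon 19 del/L858R) sensitizing mutation by plasma".

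**The concern.** PPV is a property of the assay and of the population together. With sensitivity and specificity fixed, it falls as the mutation becomes rarer. The plan measures it where the mutation has deliberately been made more common, sets a threshold for clinical usefulness on it, and words the objective for a broader group.

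The plan's argument for acting on plasma alone rests largely on specificity (sections 1.1 and 2.3). Specificity does not depend directly on prevalence and could be carried to another setting, yet section 15.4 does not ask for it. Kappa does not fill the gap, because it also depends on prevalence.

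What is at stake is the reach of a secondary conclusion. Section 2.1 says EGFR kinase inhibitors have minimal activity in wild-type disease, and sections 3.1.3 and 5.3 allow treatment on a plasma result when biopsy fails or is not feasible. A verdict of clinically useful will be read as support for that strategy, so the population it covers should be stated.

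**Working it through.** **Inputs.** Sensitivity Se = 73/97 = 0.7526 and specificity Sp = 94/95 = 0.9895 (section 2.3). These reproduce the plan's rounded 75% and 99%. Exact 95% CIs: Se 0.655 to 0.835, Sp 0.943 to 0.9997. Cohort prevalence p = 30/100 (section 15.4). The documents give no prevalence for a less selected population; 10% to 20% below is an assumed range. The plan states no expected PPV, so there is none to reproduce.

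**Formula.** PPV = Se·p / [Se·p + (1 − Sp)(1 − p)].

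**Step 1: PPV at the plan's accuracy.** At p = 0.30: 0.2258 / (0.2258 + 0.0074) = 0.968.

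| Prevalence | PPV |
|---|---|
| 30% (this cohort) | 96.8% |
| 20% (assumed) | 94.7% |
| 15% (assumed) | 92.7% |
| 12% (assumed) | 90.7% |
| 10% (assumed) | 88.8% |

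**Step 2: break-even prevalence.** PPV = 0.90 when p/(1 − p) = 9(1 − Sp)/Se = 9 × 0.010526 / 0.7526 = 0.1259, so p = 0.1259/1.1259 = 11.2%.

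**Step 3: an assay that only just passes here.** Setting PPV = 0.90 at p = 0.30 gives 1 − Sp = 0.2258/(9 × 0.70) = 0.0358, so Sp = 0.964. This lies inside the exact 95% CI for 94/95. With the same sensitivity, its PPV is 84% at 20% prevalence, 79% at 15% and 70% at 10%. Because PPV falls steadily with prevalence, it misses 90% at every prevalence below 30%.

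**Step 4: how firm the plan's specificity is.** It rests on one false positive in 95. Across its exact 95% CI, PPV runs from 0.85 to 0.999 at 30% prevalence and from 0.59 to 0.997 at 10%. Uncertainty in specificity therefore matters at least as much as prevalence.

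**Step 5: data available.** If 30 patients carry the mutation, expected plasma positives are 30 × 0.7526 + 70 × 0.0105 = 22.6 + 0.7, about 23; at 22/23 the exact 95% CI for PPV is 0.78 to 0.999. Tissue-negative patients would then number at most 70; at 69/70 the exact 95% CI for specificity is 0.92 to 0.9996. If 30 is instead the number of plasma positives (section 15.2), prevalence is (0.30 − 0.0105)/(0.7526 − 0.0105) = 0.39, which leaves at most about 61 tissue-negatives. Missing tissue lowers either figure.

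**Step 6: effect of criterion 3.1.2.1.** It admits patients whose plasma is already known to be positive at the central laboratory. For illustration, assume 10 such patients join 90 others at 30% prevalence. The 90 give 20.3 true positives, 6.7 false negatives, 0.7 false positives and 62.3 true negatives; the 10 add 9.7 true and 0.3 false positives. Apparent sensitivity becomes 30.0/36.7 = 82% instead of 75%, specificity 62.3/63.3 = 98.5% instead of 98.9%, and PPV stays at 96.8%.

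**The case against.** The strongest reply is that nothing fails on the plan's own figures unless prevalence in the wider population is under about 11%, and no section gives such a figure. At 15% and 20% the assay still passes. At 10% the shortfall is 1.2 points. This stands: a reader might infer that the assay would fail in recently diagnosed advanced NSCLC, and the documents do not support that.

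A reader might also infer that 3.1.4 alone produces the 30%. Section 15.4 credits that figure to institutional data without saying whether those patients were enriched. If 30% also held in the wider population, the gap would vanish. The stated purpose of 3.1.4 and section 3.3 is nevertheless to raise the likelihood of a mutation.

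It can also be said that objectives normally refer to the eligible population, that the synopsis describes the study population as enriched, and that no section claims the PPV for unselected patients. That is fair, and it makes part of the remedy a matter of wording. But neither the objective nor the threshold carries the limit, and the synopsis rationale presents the approach for advanced lung adenocarcinoma generally.

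Finally, kappa needs the full two-by-two table, so specificity could be derived from data already planned, and it is an aim of the separate 340-patient study. That shows the addition is cheap; it does not put specificity among the reported measures. The caution about 3.1.2.1 also stands: selection on a positive result leaves PPV intact but biases sensitivity and specificity, so the recalculation must exclude those patients.

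**Conclusion.** The point holds in a limited form. A PPV above 90% in this cohort supports a conclusion about patients meeting 3.1.4; by itself it does not establish the same for a less enriched population, which is how section 1.3 and the synopsis word the objective.

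At the plan's point estimates the consequence is small: the threshold is missed only if prevalence elsewhere is under about 11%, an assumption the documents neither supply nor exclude. The consequence is larger if true specificity is nearer 96.4%, which the plan's data allow; a bare pass here would then go with a miss at any lower prevalence. These results treat sensitivity and specificity as unchanged between populations and apply to EGFR only, not to KRAS.

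This is a minor point about interpretation and reporting. The primary endpoint, its decision rule and the sample size are untouched.

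**What to change.** 1. In sections 1.3 and 15.4 (and the synopsis objective, to match), limit the EGFR PPV conclusion to patients meeting 3.1.4.
2. In section 15.4 add specificity with an exact confidence interval, estimated from tissue-negative patients: at most about 60 to 70, fewer where tissue is lacking.
3. Beside the observed PPV, tabulate PPV recalculated from sensitivity and specificity over a stated prevalence range, for example 10% to 30%, marked as assumed.
4. Compute sensitivity and specificity without patients enrolled under 3.1.2.1 on an already known positive plasma result. They can stay in the observed PPV.

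This takes a few lines of text and one extra table, with no new data. The downside is that the PPV shown for less selected patients will look less favourable than the observed one.

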2.5 Rationale

This rapid and accurate ddPCR-based plasma genotyping assay combined with immediate treatment with erlotinib in *EGFR* mutant (exon 19 del/L858R) patients has the potential to both expedite appropriate therapy as well as avoid missed treatment opportunities in patients where tissue biopsies are delayed or not feasible. We have designed a prospective single-arm phase II study to evaluate a novel treatment strategy employing rapid plasma genotyping followed by immediate erlotinib treatment in *EGFR* mutant patients (exon 19 del/L858R) compared with standard genotyping followed by treatment. This study would specifically evaluate this novel treatment strategy compared with standard treatment with respect to the speed with which erlotinib therapy is initiated, the appropriateness of the first-line treatment initiated and overall response rate.

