4.1 General Guidelines for DF/HCC Institutions

Institutions will register eligible participants in the Clinical Trials Management System (CTMS) OnCore. Registrations must occur prior to the initiation of protocol therapy. Any participant not registered to the protocol before protocol therapy begins will be considered ineligible and registration will be denied.

An investigator will confirm eligibility criteria and a member of the study team will complete the protocol-specific eligibility checklist.

Registration on the Initial Registration arm (Step 1) occurs at the time of initial plasma genotyping. Registration to the erlotinib treatment arm (Step 2) takes place once positive EGFR mutation status is confirmed. Following registration for erlotinib treatment, participants may begin protocol therapy. Issues that would cause treatment delays should be discussed with the Overall Principal Investigator (PI). If a participant does not receive protocol therapy following registration, the participant's registration on the study must be canceled. Registration cancellations must be made in OnCore as soon as possible.

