5. STUDY PROCEDURES

5.1 Initial Plasma Genotyping

All participants will undergo a paired blood draw on the same day that they are registered in the study. Blood may be drawn the following business day if same day draw is not feasible. Three 10 mL EDTA tubes of blood will be collected at the clinical blood lab. Plasma will be prepared immediately after the blood draw, frozen and one tube transported to the central laboratory at the Brigham & Women's Hospital Center for Advanced Molecular Diagnostics (CAMD) and the two remaining tubes transported to the CONFIDENTIAL

translational research lab (TRL) at DFCI for exploratory studies (Appendix A: Plasma Preparation SOP). Extraction of cfDNA and ddPCR-based plasma genotyping for *EGFR* exon 19 del, L858R and T790M mutations will then be performed at CAMD as previously described.¹² The remaining plasma shipped to the TRL will be used for confirmatory *EGFR* plasma genotyping, *KRAS* G12X plasma genotyping and exploratory studies (9. Correlative/Special Studies). Participants with positive or pending plasma genotyping on study.

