5.3 Tissue Genotyping

All participants should undergo initial tissue genotyping on available biopsy material as per institutional standard of care at the site at which they are enrolled in the study. If available, this genotyping must be pending or ordered at the time of enrollment and must include at least testing for *EGFR* mutations and *ALK* rearrangements. If not available, a plan to obtain this tissue through biopsy must exist. If biopsy fails or is not technically feasible, patients with detectable *EGFR* mutation by plasma genotyping may still receive erlotinib on the treatment phase of the study. Targeted next-generation gene sequencing (NGS) will be requested for each patient where sufficient tissue is available but will not be a requirement for enrollment in the study. Given that tissue genotyping for *EGFR* and *ALK* are considered standard of care, the cost of these tests will not be covered by the study. Should a patient have insufficient tissue for genotyping as a part of standard of care will be left to the individual investigator based on their standard practice.

For patients that are *EGFR* mutation positive and are treated with erlotinib, re-biopsy and repeat genotyping for resistance mutations will be encouraged at the time of disease progression. The results from this testing will be collected by the study where available in order to examine rates and mechanisms of acquired resistance to erlotinib. Any biopsy done to determine tumor genotype will be considered standard of care and will not be reimbursed by the study.

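### Section 15.4 has no analysis of the first secondary objective (registration-to-treatment time, plasma versus tumor genotyping), and its order-to-result turnaround time measures a different interval.

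*Combined protocol and SAP*

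**What the plan says.** Section 1.3, repeated in the Synopsis, sets the first secondary objective: "Determine the time from study registration to treatment initiation using a rapid plasma genotyping strategy versus standard tumor genotyping". Section 2.5 restates the aim, saying that the new strategy is to be compared with standard treatment "with respect to the speed with which erlotinib therapy is initiated".

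Section 15.4 plans Cohen's kappa, positive predictive value, sensitivity and one time measure: "The turnaround time (TAT) between ordering the plasma genotyping and obtaining the result will be compared to the TAT for tumor genotyping". The two TATs are compared by a Wilcoxon test, and the plasma median is held to a target of under 3 days. No other section of the supplied text gives an estimator, comparator, analysis set or missing-data rule for time to treatment.

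Four other provisions fix the dates involved.
- **Plasma order.** Section 5.1: "All participants will undergo a paired blood draw on the same day that they are registered in the study" (the next business day is allowed). By exception, 3.1.2.1 states: "Participants with positive or pending EGFR mutation on plasma genotyping performed at the central lab are eligible for enrollment".
- **Tissue order.** Section 3.1.3: "Tissue must be available for genotyping or biopsy planned to obtain tissue for genotyping". Section 5.3, on tissue already in hand: "If available, this genotyping must be pending or ordered at the time of enrollment".
- **Treatment start.** Section 4.1 has two registrations: Step 1 at initial plasma genotyping, and Step 2 once the mutation is confirmed. Then: "Following registration for erlotinib treatment, participants may begin protocol therapy".
- **Plasma-negative patients.** Sections 6.1.1 and 6.8 keep them under observation up to the start of standard treatment.

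**The concern.** The objective is about a treatment strategy: how much sooner patients start. TAT is about an assay: how quickly a laboratory answers once asked. Followed to the letter, the plan delivers the second and nothing on the first. A time-to-treatment comparison reported later would have its comparator, time origin and handling of missing tissue results chosen after the data were seen.

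The comparator is a difficulty in itself. Plasma-positive patients start on the plasma result, so the date on which tissue would have let them start is never observed, and the plan names no substitute. Failed or infeasible biopsies matter too, because Section 2.5 names patients whose biopsies are delayed or cannot be done among those the strategy should help.

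**Working it through.** **1. The two intervals side by side**

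| | Objective (1.3) | Analysis (15.4) |
|---|---|---|
| Start | Study registration (Step 1 or Step 2 not stated) | Test order |
| End | Treatment initiation | Test result |
| Unit compared | Strategies | Assays |
| No tissue result | Not addressed | Not addressed; no TAT exists |

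The end differs for every treated patient. The start differs little for plasma, apart from 3.1.2.1 entrants. For tissue the order can come before registration (test pending) or after it (biopsy only planned).

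**2. How the quantities relate**

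For one patient let T and P be the tissue and plasma order-to-result times. Let a and b be the tissue and plasma order days minus the registration day. Let d_T and d_P be the result-to-dose times.

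- TAT gain = T − P.
- Gain in days from registration to result = (a + T) − (b + P) = (T − P) + (a − b).
- Gain in days from registration to dose = (T − P) + (a − b) + (d_T − d_P).

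Each day of a − b moves the answer by one day. With b near 0, an early tissue order (a < 0) makes the TAT gain exceed the registration-based gain, and a late one does the reverse. If central plasma was also ordered early, the lags partly cancel. In plasma-positive patients d_T is unobservable.

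**3. Illustration of the start-point term**

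From the documents: plasma TAT median 3 days, range 1–5 (Section 2.3). Assumed: lognormal tissue TAT with median 7 to 21 days and log-SD 0.4 or 0.6; plasma ordered at registration, with weights .15/.25/.25/.20/.15 on days 1 to 5; a uniform over 7 days; results falling before registration excluded.

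- Tissue ordered up to 7 days before registration: the median registration-based gain is 3.2–3.4 days smaller than the TAT gain.
- Ordered up to 7 days after: 3.6–3.7 days larger.

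Both gains stop at the result, so these figures do not size the end-point mismatch.

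**4. Illustration of failed tissue tests**

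If a fraction f of attempted tests never gives a result and these are ranked longest, the median moves to the 0.5/(1 − f) quantile of completed tests. For a lognormal the multiplier is exp(SD × z), where z is the normal quantile at that probability.

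| f (assumed) | 0.5/(1 − f) | z | Multiplier, SD 0.4 to 0.6 |
|---|---|---|---|
| 0.05 | 0.526 | 0.066 | 1.03–1.04 |
| 0.15 | 0.588 | 0.223 | 1.09–1.14 |
| 0.30 | 0.714 | 0.566 | 1.25–1.40 |

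At f = 0.30 and SD 0.6, a completed-test median of 14 days becomes 14 × 1.404 = 19.7 days.

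**5. Who must be in the comparison**

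Section 2.3 gives plasma sensitivity for exon 19 del/L858R as 73/97 (75%), so 97 − 73 = 24 of 97 carriers were missed. At that rate, 30 plasma-positive carriers imply 30 × 24/73 = 9.9 missed, and 30 carriers in total imply 30 × 24/97 = 7.4 missed. Under the plasma strategy these patients still wait for tissue. Giving them zero gain (tissue log-SD 0.6, no order lag) cuts the median gain from 4.2 to 2.5 days, 11.1 to 7.9 days and 18.1 to about 13 days for assumed tissue medians of 7, 14 and 21 days. Restricting the comparison to plasma-positive patients would therefore flatter plasma.

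**The case against.** The strongest defense is that TAT is a reasonable proxy. Blood is drawn at registration or the next business day, and treatment is meant to follow a positive result at once, so plasma order-to-result time is close to registration-to-treatment time. That largely stands for the start of the plasma interval. It does not stand for the tissue interval, whose order date is not tied to registration, and it leaves the result-to-dose step unmeasured.

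A reader might infer that Section 15.4 excludes failed tissue tests. It does not say so. It is silent, and the omission would follow only because a test without a result has no TAT. A reader might also infer that TAT exaggerates the plasma advantage. Early tissue orders push that way, while late orders and unranked failures push the other way, so the documents support no net direction. Nor are the day figures above an estimate for this trial: apart from the plasma times and the sensitivity, their inputs are assumed.

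Finally, this is a secondary objective in a single-arm phase II trial, and the success rule in Section 15.1 does not depend on it. That is correct and limits the weight of the point.

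**Conclusion.** The point holds. The first secondary objective has no planned analysis, and TAT cannot stand in for it. The end point is wrong for every treated patient, the start point is wrong mainly on the tissue side, and there is no rule for tissue tests without a result. A comparison of completed tests alone would understate tissue delay. This rests on the text and needs no simulation.

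Its size in days and its net direction cannot be derived from the documents. The primary response analysis is unaffected. The change should be made because it is cheap and because the trial otherwise has no pre-specified answer to a question it sets itself.

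**What to change.** Amend Section 15.4 as follows.

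1. Define registration as Step 1. In treated patients report days from Step 1 registration to first erlotinib dose: median, range and 95% CI.
2. Compare, within patient and from the same Step 1 origin, days to the plasma result with days to the first informative tissue result before progression, by Wilcoxon signed-rank test with the median paired difference. Label this the difference in earliest possible genotype-guided start, not in actual start. Use two stated sets: plasma-positive patients, and all mutation-positive patients. In the second set, plasma-negative, tissue-positive patients have a plasma-strategy time equal to their tissue time, so no gain. State how these zero differences are handled, since the usual signed-rank test discards them; the median difference must keep them.
3. Rank attempted tissue tests that gave no result before progression longest, with a sensitivity analysis dropping them. Do not use end-of-study or post-progression biopsies as the tissue time.
4. Report descriptively the observed registration-to-treatment times of plasma-negative, tissue-positive patients, noting that they are a selected group. Report 3.1.2.1 entrants, and patients whose biopsy was waived or not attempted, separately.
5. Keep order-to-result TAT as an assay measure.

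**Cost.** No new patients or procedures. The planned TAT comparison already needs tissue result dates, and Section 8.1.5 already records dosing start dates; tissue failure dates must be added. The plasma-positive set will hold fewer than 30 pairs: an exact CI of about 95% for a median spans the 10th to 21st ordered values of 30, the 8th to 18th of 25, or the 6th to 15th of 20. The reported plasma advantage may be smaller than the TAT difference, particularly once plasma-negative carriers are included.
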